#### **Data Resource Sharing:**

1. **DATA FORMAT:** Data will be delivered in quantitative format using SPSS software.
2. **DATA COLLECTION:** Data will be collected via print questionnaires entered into redcap data collection portals within 72 hours of collection. The unit of analysis will be the individual respondent.
3. **ASSURANCES:** Assurances, consent form, etc. will be obtained and be compliant with and reviewed by MUSC IRB.
4. **VARIABLE CREATION:** All variable creation computation syntax will be in SPSS format and delivered in txt file for reproduction by any interested party. All weighting computations will be

delivered in txt file. All imputation will be outlined and syntax delivered in txt file. A variable definition list / codebook and computational syntax document will be delivered.

PI CONTACT: Information will be included.

### **SECTION C. Procedures for Identifying, Reviewing and Reporting Adverse Events**

- 1) **Identifying.** Potential minimum risks identified for participants are outlined in the Protection of Human Subjects and will also be outlined in the IRB-approved informed consent document. Additional unknown risks may occur and, if so, will be identified through diligent monitoring by the PIs or PC throughout the conduct of this study. During the informed consent process, participants will be advised of the potential minimum risks of participation as identified in the IRB-approved informed consent document and reminded throughout the study that the researchers should be promptly informed about any concerns regarding potential side effects, adverse events, or clinical deterioration. Participants will also be instructed to notify the PI, PC, and/or designee of any suspected adverse events immediately if possible. Throughout the course of study enrollment, the researchers will maintain weekly telephone and/or face-to-face contact with the study participants to elicit information about experienced AE and to monitor participant progress. The PI or PC will maintain an electronic record of all reported adverse events and notify the DSMB of all reportable events as they occur. The DSM team will have real-time access to the study database to review and monitor all reported serious adverse events (SAE) that were reported as related to the intervention. The PI or PC will generate and provide de-identified monthly administrative human subject safety reports for the DSM team to review participant progress, accrual and attrition rates, and monitor the frequency of all reported side effects and AE. Additionally, the biostatistician will generate and provide de-identified cumulative administrative human participant semi-annual safety reports for the DSMB to review.
  
- 2) **Reviewing.** Adverse events will be assessed and graded by the members of the SMC according to the following MUSC's IRB Adverse Event Reporting Policy  
[http://academicdepartments.musc.edu/research/ori/irb/HRPP/HRPP\\_Guide\\_Section\\_4.7](http://academicdepartments.musc.edu/research/ori/irb/HRPP/HRPP_Guide_Section_4.7)
  - **Expected/Anticipated**—Identified in nature, severity, or frequency in the current protocol, informed consent, investigator brochure, or with other current risk information.
  - **Unexpected/Unanticipated**—Not identified in nature, severity, or frequency in the current protocol, informed consent, investigator brochure, or with other current risk information.
  - **More Prevalent**—Occurs more frequently than anticipated or at a higher prevalence than expected.
  - **Serious**—Results in death, is life threatening, requires inpatient hospitalization or prolongs existing hospitalization, results in persistent or significant disability/incapacity, cancer, overdose, or causes a congenital anomaly/birth defect. The relationship of adverse events to study participation will be determined by the SMC according to the MUSC IRB Adverse Event Reporting Policy:
  - **Unrelated**—There is not a reasonable possibility that the adverse event may have been caused by the drug, device or intervention.
  - **Possibly Related**—The adverse event may have been caused by the drug, device, or intervention, however there is insufficient information to determine the likelihood of this possibility.
  - **Related**—There is a reasonable possibility that the adverse event may have been caused by the drug, device or intervention.
  
- 3) **Reporting.** All reportable AE, SAE and unanticipated problems experienced by participants will be reported to the NIH and MUSC IRB in compliance with their Adverse Event Reporting Policy requirements, using the IRB's password protected on-line secure server adverse event reporting system. Within 24 hours after a reportable AE, SAE or unanticipated problem has been reported by the participant, it will be graded by the PI or PC and submitted by the PI to MUSC IRB. After IRB review and acknowledgement, the PIs or PC will forward a copy of the reportable AE, SAE or unanticipated problem and IRB acknowledgement letter to the NIH Program Officer through MUSC's

OSRP within 24 hours. In addition, all cumulative reportable AE, SAE and unanticipated problems included in the DSMB reports will be submitted to the NIH in the PI's Annual Progress Reports.

**4) Definitions of Potential Reportable Adverse Events.** In accordance with MUSC IRB Adverse Event Reporting Policy, an AE is reportable if it meets all of the following criteria: 1) is unexpected 2) is related and/or possibly related, and 3) is serious and/or suggests that the research places subjects or others at a greater risk of physical or psychological harm than was previously known or recognized. Additionally, per MUSC's policy all participant deaths, protocol deviations, complaints about the research, and breaches of confidentiality are reportable events. In this study we will use the FDA definition of serious adverse events (SAEs). SAEs will be systematically assessed at each clinic visit. Any SAE, whether or not related to study intervention, will be reported to the IRB and NIH. The initial SAE report will be followed by submission of a completed SAE report to both institutions. In the event that a client either withdraws from the study or the investigator decides to discontinue a patient due to SAE, the client will be monitored by the investigators via ongoing status assessment until 1) a resolution is reached i.e., the problem requiring hospitalization has resolved or stabilized with no further changes expected 2) the SAE is determined to be clearly unrelated to the study intervention, or 3) the SAE results in death. Outcome of SAEs will be periodically reported to NIH. A summary of the SAEs that occurred during the previous year will be included in the annual progress report to NIH. During screening, study applicants will undergo a baseline assessment to determine their eligibility and safety of their participation in this study. History of suicidal ideation or suicide attempts, and other suicidal risk factors, including suicidal ideation, intent, and plan will be carefully assessed and monitored through the study. The PI, who is a licensed clinical psychologist, will be contacted immediately regarding clients who are at risk to commit suicide to aid in safety assessment (as described in Human Subjects plan) and will be offered additional treatment (e.g., hospitalization) as needed and appropriate. As noted above, all adverse effects of the interventions, assessment procedures, or any aspect of the study will be documented and reported within 24 hours to the University IRB and the Project Officer(s).

#### **SECTION D. Assessment of External Factors**

The PI will conduct a semiannual assessment of external factors through a review of literature related to new developments in the areas of HIV adherence, PTSD symptom management (including avoidant coping and stigma), symptom reporting and other approaches that may have an impact on the safety of participants or on the ethics of the study. To determine whether any changes are necessitated to the study protocol, DSMB will review any identified literature or product safety data that may pose as a potential impact to the risk benefit ratio study and/or safety of study participants.

#### **SECTION E. Interim Analysis**

This study aims to test the feasibility and acceptability of an integrated, evidence-based protocol for PTSD and adherence for PLWH within a HIV care clinic. To our knowledge, there are no similar studies specifically designed for this patient population and purpose. As such, the biostatistician will generate semi-annual qualitative interim analysis reports on a) adverse events; and b) data obtained during phone call and returned end-of-study surveys to understand issues related to the uptake, usability, and adoption of this intervention among this population. We will evaluate the screening and enrollment procedures, barriers to participation and retention, including, safety, adherence, acceptability, problems encountered, if any, and feedback from the participants and the case managers. This information gained from this structured process will be used to both guide the refinement of the current protocol and to inform the design of a larger efficacy trial. Interim analysis of outcome variables (e.g., PTSD symptoms, ART adherence, viral load) was not considered to avoid inexact inferences and increased chance of error due to few data points, as well as potential for bias if interim results were known to the investigators. Therefore, there are no planned stopping rules for this study.

#### **14.0 Withdrawal of Subjects**

Participants may voluntarily elect to withdraw their consent at any time for any or no given reason while enrolled in the study. The PI may withdraw participants from the study at any time if they decide it is in

the participant's best interest, if they do not follow the investigator's instructions, and/or if they fail to maintain to contact with the researchers or attend study visits. Withdrawals of participants may also occur if there is a protocol violation or early study closure. All data gathered from withdrawn participants will be used in the analysis plan under an Intention-to-Treat (ITT) model.

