## 4.0 Study Endpoints

Study end points for both Aims I and II include: successful study completion, participant consent withdrawal, and PI termination due to failure to adhere to the protocol, loss of contact with the participant, and/or unexpected adverse events.

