Randomization Procedures. For Aim 2, we will use an adaptive randomization procedure (urn randomization) to balance confounding variables among participants in each condition. Factors on which the adaptive randomization procedure will operate are viral load and self-identified gender. Computerized urn randomization will use an adaptation of Microsoft Access application gRand (used by Co-I [name]). Efforts will be made to keep the project coordinator (PC) blind to condition, therefore, PI [name] will randomize participants. Participants will be randomized following consent and baseline assessment (to determine severity of symptoms for the urn) to one of two conditions: (1) CPT-L + Standard of Care (SOC) or (2) Lifesteps + SOC. Within 7 days of interview and PI's randomization, the PI will contact the participant to inform him/her of condition. Case managers will do phone check-ins between sessions to encourage attendance and provide referrals and information to individuals in both CPT-L and Lifesteps groups. Individuals in the Lifesteps condition will receive the one-session adherence intervention in addition to any other standard treatment that a PLWH with PTSD symptoms would typically receive at a HIV care clinic. SOC treatment will vary in type, duration, and frequency (e.g.,

spiritual counseling, crisis hotline phone call, resource help for case manager,), but will be measured carefully across both conditions through coding of chart review and weekly electronic dairy assessment of service utilization (methods used successfully by Co-I [name] in prior RCTs) to account for Treatment dosage. Baseline, post-intervention and follow-up assessments will be collected by the PC. In the CPT-L condition, the PI, assigned case manager, and project therapist will make contact within 7 days of randomization. Participants in the control condition will be contacted by one of the Lifesteps-trained HIV care case managers.

Figure 2. Participant Flow Diagram

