**Assessments and Data Collection Procedures.** The PC (blind to condition) will conduct the initial eligibility (baseline) diagnostic assessments and all study assessments. The CAPS will be audio-taped and study personnel will listen to a randomly selected 20% to ensure reliability of CAPS diagnosis over the course of the study. The PC will administer the battery in the HIV care clinic or remotely by phone to the participant, based on participant preference. All timepoints will be collected on all participants, even if they drop out of treatment. Pilot trials indicate that major assessments take between 1.5 – 2 hours to complete. Individuals will be given \$50 for completing the baseline interview, \$40 for attending the first session, then \$60 for post-intervention assessments and 20-minute exit interview after completion of CPT-L sessions (i.e., post intervention ~6 weeks after study enrollment); and a \$75 gift card for 3 month follow up surveys. Several questionnaires were drawn from the PROMIS common data elements and NIH sponsored repositories to promote data sharing (e.g., PROMIS depression and BRICS Social Determinants of Health). Participants will complete a brief electronic diary on a weekly basis to assess use of resources/additional supports. Research has demonstrated the validity of this approach, including capturing “real-time” data beyond what can be captured with retrospective reports. Surveys (<1 minute each) will be electronically collected once a week for the 6 weeks of the intervention period starting one week after randomization (i.e., 6 electronic survey entries), leading up to the 3-month follow up. With input from the CAB, we have established procedures to auto-send an email or SMS text (participant choice) on a set schedule. SMS text messaging is possible via Twilio, embedded within our REDCap system, which allows participants to complete a survey directly from their phone, without having to access a webpage. Participants will be asked permission for the study team to access electronic medical records to collect CD4 count and viral load at the time of enrollment. As an attending physician in the clinic, Co-I [name] is familiar with these electronic records and will oversee the data pull. CD4 T-cell counts and HIV viral load will be measured as standard clinical practice using standard clinical assays (HIV viral load less than 200 considered virologic suppression). Relevant data from the clinic’s electronic medical record (e.g., CD4 count, no-shows) will be collected at intervals and study completion (i.e., 6 months after participation) to document retention in HIV clinical care using the industry standard of 2 appointments with a provider with prescribing privileges per year, no longer than 6 months apart. PI [name] has planned for adequate staff training and coverage based on experience. The PI will assist in training research staff on consent, diagnostic interview, assessment measures, and medical chart data retrieval (with Co-I [name] and Co-I [name] for service utilization data) and will conduct weekly meetings, quarterly reviews, and booster trainings to ensure standardized procedures. See Table 2 for research instruments.

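### The PI, who knows allocation, may withdraw participants from the study for non-compliance or missed visits, and the plan does not say that outcome assessment then continues

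*Combined protocol and SAP*

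**What the plan says.** Section 14.0 (Withdrawal of Subjects) gives the PI discretion to withdraw people from the study, not merely from treatment. Besides the participant's own interest, the PI may do so for failure to comply with instructions or "if they fail to maintain to contact with the researchers or attend study visits". It adds: "Withdrawals of participants may also occur if there is a protocol violation or early study closure". No number of missed visits and no degree of non-compliance is set. The section closes by saying that what has been collected from withdrawn people will be analysed by intention to treat.

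Section 4.0 (Study Endpoints) lists, beside completion and withdrawal of consent, "PI termination due to failure to adhere to the protocol, loss of contact with the participant, and/or unexpected adverse events" for both aims.

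Section 10.0 (Study Design / Methods), under assessments and data collection, says: "All timepoints will be collected on all participants, even if they drop out of treatment". Under randomization procedures, the same section says that the PI "will randomize participants" so that the project coordinator can be kept blind, and that the PI then tells each person the assigned condition.

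**The concern.** The grounds for withdrawal lie close to what the trial measures: clinic attendance, ART adherence, viral load and retention. Someone withdrawn for not attending or not complying is likely to differ on those outcomes from someone who stays. If withdrawal also ends assessment, later outcomes are missing for reasons related to their values. Intention-to-treat analysis of what was collected cannot supply outcomes that were never collected. The Aim 2 analysis text in section 12.0 names no missing-data method for them.

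Three features of the design raise the risk. The person deciding knows the arm. The burden differs: section 3.0 gives CPT-L 12 sessions of 90 minutes with homework, against one Lifesteps session in control. And section 5.0 admits people because they missed an HIV care appointment or report under 90% adherence, so behaviour resembling the withdrawal grounds will be common.

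The trial is a pilot, but sections 1.0 and 12.0 use it to supply effect indicators and variability estimates for the next trial. Selective loss would carry into that design.

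**Working it through.** **Step 1: the text side by side.**

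| Place | What it settles | What it leaves open |
|---|---|---|
| 10.0, assessments | All timepoints, everyone, including those who stop treatment | Whether this covers people the PI removes from the study |
| 14.0 | The PI may withdraw from the study; data already held are analysed | Whether assessment continues after withdrawal |
| 4.0 | PI termination is one way participation ends | The same |
| 10.0, randomization | The PI knows the arm | No allocation-blind review of withdrawals is required |

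There are two readings. If the section 10.0 promise covers everyone, then sections 4.0 and 14.0 should say that follow-up continues. If it covers only people who stop treatment, PI withdrawal leaves a gap. The documents do not choose between them.

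**Step 2: the plan's own precision.** Section 12.0 assumes detectable viral load of 10% with CPT-L and 20% with Lifesteps, 30 per arm, and states an interval of 18 points either side of the difference. Check:

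1.96 × √(0.10×0.90/30 + 0.20×0.80/30) = 17.9 points, which agrees.

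With three CPT-L participants lost (27 against 30): 1.96 × √(0.09/27 + 0.16/30) = 18.2 points. A few losses hardly change precision, so the issue is bias.

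**Step 3: possible bias.** Assumptions, not document figures: 6/30 (20%) truly detectable in both arms, no true effect, a complete control arm, and three CPT-L participants lost, of whom d are detectable. The observed CPT-L rate is (6 − d)/27, and the false difference is that rate minus 20%.

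| Detectable among the three lost | Observed CPT-L rate | False difference |
|---|---|---|
| 0 | 6/27 = 22.2% | +2.2 points |
| 0.6 (the arm rate, 20%) | 5.4/27 = 20.0% | 0 |
| 1.5 (half) | 4.5/27 = 16.7% | −3.3 points |
| 3 (all) | 3/27 = 11.1% | −8.9 points |

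If three detectable participants leave each arm, 3/27 − 3/27 = 0.

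**Step 4: exposure to the rule.** If a missed therapy session counted as a ground, the chance of at least one miss would be 1 − (1 − p)^12 for CPT-L and p for control. The per-session miss rate p is an assumption.

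| p | CPT-L, 12 sessions | Control, 1 session |
|---|---|---|
| 2% | 22% | 2% |
| 5% | 46% | 5% |
| 10% | 72% | 10% |

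This shows unequal opportunity under that reading only. It does not show unequal withdrawal.

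**Step 5: which outcomes are exposed.** In Table 2, CAPS-5, PCL and self-reported ART adherence need the participant. Viral load, CD4 count and clinic attendance come from the medical record and could still be collected if consent stands. The Step 3 example uses viral load because section 12.0 gives planning rates for it. The same arithmetic applies to any yes/no outcome, and the outcomes that need contact are the more exposed.

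**The case against.** The strongest reply is that section 10.0 already promises full collection, and that its clause about stopping treatment extends the promise rather than limits it. On that reading nothing is lost. This is a fair reading, and no text says that assessment stops when the PI withdraws someone. But section 14.0 speaks of leaving the study and section 4.0 ranks PI termination with withdrawal of consent, so staff could equally stop assessing.

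A reader might infer that the rule removes poor adherers unequally and so favours CPT-L. The documents do not support that. The wording is permissive and gives no arm-specific rule. The visits in section 14.0 may be assessment visits, and Table 2 sets one assessment schedule for both arms. The argument from 12 sessions against one has force only if missed sessions or homework count as not following instructions, which is not stated.

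A reader might also infer that the PI can flatter the retention benchmark. Section 12.0 defines retention as a share of randomised patients, so withdrawn people already count against it: six withdrawals would use up the 10% allowance (6/60).

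Two further points stand in part. Someone who cannot be reached cannot be interviewed, whatever the label. And section 13.0 provides for reports on retention, disposition and attrition, which makes withdrawals visible but does not recover outcomes.

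**Conclusion.** The point holds as an unreconciled rule with a real route to selective loss, not as demonstrated bias. Sections 4.0, 10.0 and 14.0 do not together say whether outcomes are collected after PI withdrawal, and the person deciding knows the arm.

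The size depends on assumptions that the documents cannot settle: that withdrawal ends assessment, how many are withdrawn, from which arm, and how they would have fared. For three one-sided losses from CPT-L at a 20% rate, the illustration runs from 0 (losses at the arm rate) to −8.9 points (all detectable). It turns slightly positive if none is detectable and is 0 if losses are balanced. The −8.9 figure is close to the 10-point planning difference and tempting to quote alone. It is a one-sided worst case on an outcome that could still be read from the record, and about half the plan's own 18-point margin. It should not be presented as the expected effect.

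The change is worth making because applying the rule as written could lose outcomes selectively and preventing that costs little.

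**What to change.** In sections 4.0 and 14.0, and consistently with section 10.0:

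- Separate stopping study treatment from leaving the study.
- State that non-compliance, missed sessions or visits, and protocol violations do not end outcome assessment.
- Continue to attempt the post-intervention, 3-month and record-based assessments unless the participant withdraws consent.
- Report PI withdrawals and their reasons by arm.

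The rules for stopping treatment itself are not touched by this point and remain for the study team. The cost is protocol wording and a few extra follow-up contacts; the record-based outcomes need none.
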